6.8 Assessment of Safety

Any patient who receives at least one dose of study medication on this protocol will be evaluable for toxicity, with toxicity evaluated using the National Cancer Institute (NCI) Common Terminology Criteria for Adverse Events (CTCAE), version 4.0 available at:
http://ctep.cancer.gov/protocolDevelopment/electronic_applications/ctc.htm

6.9 Assessment of Primary Endpoint and Efficacy

Provided sufficient tumor tissue is available pre and post treatment (specifically at progression) to perform kinomining, data from the patient will be utilized to inform the primary objective. If a patient drops out of the study prior to progression, they may be replaced. See section 4.9 for additional information. For subjects who are withdrawn from study treatment, but are later placed back on the trametinib/dabrafenib combination therapy, a biopsy may be collected from the former study subject at the time of progression from the standard of care trametinib/dabrafenib therapy. Information from these biopsies will be included in the analysis of the primary objective and the correlative secondary objective.

Patients who have received at least 2 cycles of therapy and have their disease re-evaluated after 2 cycles will be evaluable for assessment of objective response. Patients who drop out of the study prior to this point will not be evaluable for response unless their disease progressed prior to this point.

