1.5.1 Summary Safety Information of the Combination

Most subjects treated with combination therapy experienced an adverse event. In both studies, pyrexia was the most frequently reported AE, and the most frequently reported grade 3 event (presented with *) in subjects treated with combination therapy (51%/6%*) in Study MEK115306 and 57%/4%* in Study BRF113220). AEs that occurred in >30% of subjects treated with combination therapy in either study included pyrexia, fatigue, vomiting, chills, nausea, and headache.

Grade 4 AEs reported in more than a single subject treated with combination therapy included neutropenia (3 subjects in Study BRF113220) pyrexia (2 subjects in Study BRF113220). AEs leading to permanent discontinuation were reported in <10% of subjects treated with combination therapy in either study.

The most common SAEs in both studies were pyrexia and chills. Fatal SAEs have been reported in 4 subjects in the combination therapy arm in Study MEK115306 and 3 subjects in the 3 subjects in the 150mg/2mg combination therapy arm in the Study BRF113220 pooled combination therapy population. One fatal SAE was reported in 2 subjects in Study MEK115306 (cerebral hemorrhage).

In general, the overall profile of AEs of special interest observed in subjects treated with combination therapy is consistent with the known profiles of each separate drug. The most notable differences were the increase in Grade 3 pyrexia and hepatic events and the decrease in skin-related toxicities with combination therapy relative to monotherapy.

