4.0 TREATMENT PLAN

4.1 Schema

^aPatient must have tumor accessible to biopsy to be eligible if frozen tissue from diagnostic specimen is not available.

^bPatient may remain on treatment after progression if evidence of continuing clinical benefit

^cClinical or radiological

^dReasons may include, but are not limited to, inability to tolerate the combination of dabrafenib and trametinib, receiving other therapy, or completion of 3-years of study treatment without progression

^eThe subject may be placed back on the combination trametinib/dabrafenib therapy as part of his/her standard of care treatment plan

^fThe subject may have a progression biopsy taken after progression on standard of care treatment if the subject is eligible and consents to this biopsy. Progression can be defined clinically or radiologically.

This is an open label study of patients with unresectable stage III and stage IV melanoma with mutant V 600E/K melanoma and tumor that is accessible to biopsy. Patients can have had any number of prior lines of treatment (and may be previously untreated), but may not have previously received either a BRAF or MEK inhibitor for treatment of their melanoma.

Patients will receive the BRAF inhibitor dabrafenib and MEK inhibitor trametinib orally at the RP2D determined in the Phase I/II study (BRF113220): trametinib 2mg QD and dabrafenib 150 mg BID on a continuous basis. A cycle will be defined as 3 weeks in duration. Cycles will be repeated until disease progression (clinical or radiological). Patients may remain on treatment after progression (at the discretion of the investigator) as long as they are still experiencing clinical benefit. Patients will be requested to remain on study medication until the biopsy at progression is performed.

Patients will have a biopsy at baseline and at progression. Some subjects may be removed from study prior to progression for other reasons that include, but are not limited to, an inability to tolerate the combination of dabrafenib and trametinib, a need to receive other therapy, or completion of 3-years of study treatment without progression. If one of these subjects later receives the combination of dabrafenib and trametinib per his/her standard of care treatment plan, then the subject may re-consented for a biopsy upon progression. These subjects are required to consent to re-enter the study for the purposes of having a progression biopsy.

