4.9 Patient Replacement

If a patient drops out of the study prior to progression, they may be replaced after consultation with the manufacturer of trametinib and dabrafenib, GSK. We anticipate that ≤ 3 patients will fall into this category.

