6.3 Treatment Assessments

6.3.1 Day 1 of each 3-week cycle until cycle 9, and then D1 of every odd numbered cycle thereafter

Clinical evaluation: focused history, physical examination (to also include vital signs, and weight), and ECOG performance status.

Laboratory studies:

- **Hematology**: Hematology includes the following parameters: complete blood count (CBC) with differential, hemoglobin (Hgb), and platelet count.
- **Serum Chemistries and LFTs**: These include the following parameters: creatinine, sodium, potassium, calcium, magnesium, phosphorus, LDH, albumin, total bilirubin, AST (SGOT) and ALT (SGPT).

Concomitant medications: Review any additions or deletions

Patient Diary: Review Diary

Toxicity Assessment: Using NCI CTCAEv4; toxicity assessment should include interrogation of the patient related to any visual changes they may be experiencing.

6.3.2 Day 1 of every other 3-week cycle starting with Cycle 3 until end of treatment

Clinical evaluation: Dermatologic exam

Tumor measurement: Tumor measurement or imaging should remain consistent throughout study, and will include contrasted computed tomography (CT) scan of chest, abdomen and pelvis. These tests may be performed ± 7 days of the scheduled day.

Note: The frequency of tumor assessment scans reduced to every 12 weeks for subjects responding to combination therapy after cycle 9; For subjects responding to combination therapy for > 2 years, the frequency of disease assessment scans should be reduced to every 6 months.

6.3.3 Day 1 of Cycles 3, 5, 9, 13 and every 4th cycle thereafter

Cardiac monitoring: 12-lead ECG and ECHO

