univariate analysis of kinase expression will be carried out to identify differentially expressed kinases after FDR adjustment. Since multiple kinases work in concert to regulate their functions, prediction analysis of microarrays (PAM) based on nearest shrunken centroid [9] will also be carried out to identify a subset of kinases that predicts resistance to BRAF+MEK inhibition. We also plan to utilize the kinome pathway as prior information in the analysis for identifying functionally related kinase sets to improve statistical power. Focusing on kinase sets may yield more reproducible and interpretable results.

Fisher's exact test will be carried out to test for association between the mutations at baseline to mutations upon the development of resistance to BRAF + MEK inhibition in each oncogene/tumor suppressor gene. Tumor samples from patients who progress while on study and those who are removed from study and who later progress on the combination treatment will be analyzed as one data set. The p-values will be adjusted via FDR to account for multiple comparisons.

The response rate will be estimated and 95% confidence interval will be computed. Progression-free survival will be evaluated using the Kaplan-Meier method. All demographic and analytic data will be summarized by descriptive statistics. Categorical data will be summarized using frequency tables whereas summary statistics such as means, medians, standard deviation and range will be provided for continuous data.

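### The response rate leaves out treated patients who stop before the week-6 re-evaluation without progression, so it can only equal or exceed the all-treated rate, by about 0 to 8 points for 0 to 2 such patients

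*Combined protocol and SAP*

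**What the plan says.** Section 2.2.2 makes the overall response rate (complete plus partial response, RECIST 1.1) a secondary objective. Section 6.9 sets the entry condition for the response analysis: "Patients who have received at least 2 cycles of therapy and have their disease re-evaluated after 2 cycles will be evaluable". It then deals with those who leave sooner: "Patients who drop out of the study prior to this point will not be evaluable for response unless their disease progressed prior to this point".

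Section 4.1 defines a cycle as 3 weeks. Section 6.3.2 places tumor measurement on "Day 1 of every other 3-week cycle starting with Cycle 3 until end of treatment", so the first scheduled on-treatment assessment falls at about week 6.

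On the analysis, Section 8.1 says only this: "The response rate will be estimated and 95% confidence interval will be computed". It names neither a denominator nor an all-treated analysis. The best-response table in Section 6.9.5 has an inevaluable category, but nothing says whether those patients count in the rate. A treated population is defined in Section 6.8, for safety only: "Any patient who receives at least one dose of study medication on this protocol will be evaluable for toxicity". Section 4.9 adds "If a patient drops out of the study prior to progression, they may be replaced", after consultation with the manufacturer, and anticipates no more than 3 such patients.

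**The concern.** The evaluability rule depends on what happens after treatment starts. Section 4.1 accepts clinical as well as radiological progression, so patients who fail early by progressing are kept, which is right. Those removed stop for toxicity, withdraw, or die with no progression recorded before the first re-evaluation. None of them would be counted as a responder, so removing them shrinks the denominator and leaves the numerator alone.

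The reported rate and its interval would then describe patients who reached the first re-evaluation or progressed, not everyone who started the combination. Early intolerance would not show in the efficacy figure. The confidence interval does not reflect this selection, and in a trial of 20 each exclusion moves the estimate by about 4 points. A reader is likely to set the result beside the earlier response rates quoted in Sections 1.5.5 (76%) and 1.7 (81%).

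**Working it through.** The plan states no precision or sample size for the response rate, so it has no figure of its own to reproduce. Table 1 in Section 8.1 concerns the kinase comparison only.

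**Direction.** Three provisions together keep an early leaver from counting as a responder:

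- No tumor measurement is scheduled before Day 1 of Cycle 3 (6.3.2).
- Best response is limited to the treatment period (6.9.5).
- In the 6.9.5 table, a complete or partial response followed by an inevaluable time point becomes stable disease or inevaluable.

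Let x be the number of responders and k the number of excluded early leavers. The numerator is the same under both definitions, and the 6.9 denominator is smaller by k.

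**Inputs**

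- Planned size: 20 patients (1.1, 1.7).
- Responders: x = 15, an assumption close to the 76% in 1.5.5.
- Number excluded: k is not given. Section 1.5.1 reports for two earlier studies that "AEs leading to permanent discontinuation were reported in <10% of subjects treated with combination therapy in either study". Applied to 20 patients, that is fewer than 2, at any time on treatment and for adverse events only. Withdrawals and deaths before week 6 would add to it. I take k = 0 to 2. The value k = 3 is an upper bound, because the figure in 4.9 covers drop-out at any time before progression.

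**Case A: 20 treated, no replacement.** Gap = x/(20 − k) − x/20. Intervals are exact (Clopper-Pearson).

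| k | All-treated | Under 6.9 | Exact 95% CI under 6.9 | Gap (points) |
|---|---|---|---|---|
| 0 | 15/20 = 75.0% | 15/20 = 75.0% | 50.9 to 91.3 | 0 |
| 1 | 75.0% | 15/19 = 78.9% | 54.4 to 93.9 | 3.9 |
| 2 | 75.0% | 15/18 = 83.3% | 58.6 to 96.4 | 8.3 |
| 3 (upper bound) | 75.0% | 15/17 = 88.2% | 63.6 to 98.5 | 13.2 |

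**Case B: leavers replaced until 20 are evaluable.** Gap = x/20 − x/(20 + k).

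| k | Under 6.9 | All-treated | Exact 95% CI, all-treated | Gap (points) |
|---|---|---|---|---|
| 1 | 15/20 = 75.0% | 15/21 = 71.4% | 47.8 to 88.7 | 3.6 |
| 2 | 75.0% | 15/22 = 68.2% | 45.1 to 86.1 | 6.8 |

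Replacement restores the number evaluable but does not close the gap.

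**Sensitivity to the response rate (no replacement).** With 16 responders of 20, the gap is 4.2 points for k = 1 (84.2% against 80.0%) and 8.9 for k = 2 (88.9% against 80.0%). Using the cited rates directly with k = 2:

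- If 76% or 81% is the evaluable rate p, the gap is p × 2/20 = 7.6 or 8.1 points.
- If it is the all-treated rate, the gap is p × 2/18 = 8.4 or 9.0 points.

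**The case against.** The strongest reply is that 6.9 is a prespecified definition, not a mistake. It already keeps early progressors, and nothing in the documents contradicts it. Counting unobserved patients as non-responders is itself a convention. If early leavers would have responded as often as the others, the all-treated figure understates activity, so the gap is a distance between two estimands and not a demonstrated bias. That stands. It is why the finding is a one-directional difference and the evaluable rate should be kept.

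Second, the exclusion sentence speaks of leaving the study, while Sections 4.8 and 4.10 separate stopping therapy from leaving the study, and 4.7 and 6.6 record available scans after therapy stops. The distinction is fair but does not rescue these patients. The preceding sentence in 6.9 requires two cycles and a re-evaluation, and so excludes early toxicity stops and early deaths whether or not they count as having dropped out.

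Third, the size rests on an assumed count. No passage gives the number leaving before week 6, and therapy may last up to 3 years (4.6), so most discontinuations could come later. Zero or one exclusion is quite possible, and zero means no gap. This stands.

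Fourth, replacement is optional and is discussed mainly for the kinome objective. True, but neither 4.9 nor 6.9 brings a replaced patient back into the response rate.

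Last, the consequence is modest. The endpoint is secondary, with no threshold or stopping rule; all dosed patients are evaluable for toxicity (6.8); and 4 points is small beside an interval about 40 points wide. This limits the priority of the point but does not remove it: the shift has one direction, and the denominator in 8.1 is unnamed in any case.

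**Conclusion.** The concern holds. Followed as written, the plan gives a response rate conditioned on reaching the first re-evaluation or progressing, and that rate cannot fall below the all-treated rate when unobserved responses count as non-responses. The expected excess is about 0 to 8 points without replacement, and about 4 to 7 points if one or two leavers are replaced. This rests on two assumptions: 0 to 2 early leavers without progression, and a true rate near those the protocol cites. The existence and direction of the effect are firm; its size is not. The primary kinome analysis is unaffected. The change is worth making because it costs almost nothing, not because a conclusion of the trial turns on it.

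**What to change.** In Sections 6.9 and 8.1:

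- Define the main response-rate denominator as all patients who received at least one dose, the population already used in 6.8.
- Count patients without an evaluable post-baseline assessment as non-responders. This also settles how the inevaluable category in 6.9.5 is handled.
- Include replaced patients as well as their replacements.
- Report the exact 95% confidence interval.
- Keep the response-evaluable rate as a supportive figure, with both denominators shown.

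The cost is one or two sentences, with no new data and no change to patient management. The headline rate may be slightly lower, and it is conservative for patients whose response was not observed.

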6.9.1 Assessment of Disease-Tumor Measurement Based on RECIST 1.1

See the international criteria proposed by the Response Evaluation Criteria in Solid Tumors (RECIST) Committee, version 1.1 (Eur J Cancer 45;2009:228-247) for additional details on RECIST1.1.

Measurable disease will be defined as the presence of at least one measurable lesion that can be accurately measured in at least one dimension with the longest diameter a minimum size of:

- ≥ 10 mm by CT scan (CT scan slice thickness no greater than 5 mm)

- 10mm caliper measurement by clinical exam (lesions which cannot be accurately measured with calipers should be recorded as non-measurable).
- 20 mm by chest x-ray.

For malignant lymph nodes to be considered pathologically enlarged and measurable, a lymph node must be ≥ 15 mm in short axis when assessed by CT scan (CT scan slice thickness recommended to be no greater than 5mm). At baseline and in follow-up, only the short axis will be measured and followed.

All other lesions, including small lesions (longest diameter < 10 mm or pathological lymph nodes with ≥ 10 to < 15 mm short axis) as well as truly non-measurable lesions, will be considered non-measurable. Lesions considered truly non-measurable include leptomeningeal disease; ascites; pleural/pericardial effusion; inflammatory breast disease; lymphangitic involvement of skin or lung, abdominal masses/abdominal organomegaly identified by physical exam that is not measurable by reproducible imaging techniques.

All measurements should be recorded in metric notation, using calipers if clinically assessed. All baseline evaluations should be performed as close as possible to the treatment start and never more than 4 weeks before the beginning of the treatment. The same method of assessment and the same technique should be used to characterize each identified and reported lesion at baseline and during follow-up. Imaging based evaluation should always be done rather than clinical examination unless the lesion(s) being followed cannot be imaged but are assessable by clinical exam. Clinical lesions will only be considered measurable when they are superficial and ≥ 10 mm diameter as assessed using calipers (e.g. skin nodules). For the case of skin lesions, documentation by color photography including a ruler to estimate the size of the lesions is recommended.

6.9.2 Baseline Documentation of Target and Non-Target Lesions

All measurable lesions up to a maximum of 5 lesions total (and a maximum of two lesions per organ) representative of all involved organs should be identified as target lesions and will be recorded and measured at baseline.

Target lesions should be selected on the basis of their size (lesions with the longer diameter), be representative of all involved organs, but in addition should be those that lend themselves to reproducible repeated measurements.

A sum of the diameters (longest for non-nodal lesions, short axis for nodal lesions) for all target lesions will be calculated and reported as the baseline sum diameters. If lymph nodes are to be included in the sum, only the short axis is added into the sum. The baseline sum diameters will be used as reference to further characterize the objective tumor response of the measurable dimension of the disease.

All other lesions (or sites of disease) including pathological lymph nodes should be identified as non-target lesions and should also be recorded at baseline. Measurements are not required and these lesions should be followed as “present” or “absent”, or in rare cases “unequivocal progression”.

6.9.3 Evaluation of Target Lesions using RECIST 1.1 Criteria

NOTE: Whenever possible, a biopsied lesion should not be considered a target lesion for RECIST tumor assessments. If the biopsied lesion is the only site of measurable disease, it may only be followed as a target lesion if a core biopsy was performed. Lesions that have been completely removed or subjected to excisional biopsy should not be followed as target lesions.

NOTE: In addition to the information below, also see section 4.3.2 in the international criteria proposed by the Response Evaluation Criteria in Solid Tumors (RECIST) Committee, version 1.1 (Eur J Cancer 45;2009:228-247) for special notes on the assessment of target lesions.

Complete response (CR)—Disappearance of all target lesions. Any pathological lymph node (LN) target or no must have decreased in short axis to <10mm.

Partial response (PR)—At least a 30% decrease in the sum of the LD of the target lesions taking as reference the baseline sum LD.

Progressive Disease (PD)—At least a 20% increase in the sum of the LD of the target lesions taking as reference the smallest sum LD recorded since the treatment started including baseline if that is the smallest on study. In addition to the relative increase of 20%, the sum must also demonstrate an absolute increase of at least 5mm. The appearance of one or more new lesions also constitutes PD.

Stable disease (SD)—Neither sufficient shrinkage to qualify for PR nor sufficient increase to qualify for PD taking as references the smallest sum LD since the treatment started.

6.9.4 Evaluation of Non-Target Lesions using RECIST 1.1 Criteria

Complete response (CR)—Disappearance of all non-target lesions and normalization of tumor marker levels. All LN must be non-pathological in size (<10mm short axis).

Non-complete response (non-CR)/non-progression (non-PD)—Persistence of one or more non-target lesion(s) or/and maintenance of tumor marker level above the normal limits.

Progressive disease (PD)—Appearance of one or more new lesions and/or unequivocal progression of existing non-target lesions.

6.9.5 Evaluation of Best Overall Response using RECIST 1.1 Criteria

The best overall response is the best response recorded from the start of the study treatment until the end of treatment. The best overall response will be defined according to the following table.

Overall Response First Time Point	Overall Response Subsequent Time Point	BEST Overall Response
CR	CR	CR
CR	PR	SD, PD, or PR ¹
CR	SD	SD provided minimum criteria for SD duration met, otherwise, PD
CR	PD	SD provided minimum criteria for SD duration met, otherwise, PD
CR	NE ²	SD provided minimum criteria for SD duration met, otherwise, NE ²
PR	CR	PR
PR	PR	PR
PR	SD	SD
PR	PD	SD provided minimum criteria for SD duration met, otherwise, PD
PR	NE ²	SD provided minimum criteria for SD duration met, otherwise, NE ²
NE	NE ²	NE ²

¹ If a CR is truly met at first time point, then any disease seen at a subsequent time point, even disease meeting PR criteria relative to baseline, makes the disease PD at that point (since disease must have reappeared after CR). Best response would depend on whether minimum duration for SD was met. However, sometimes 'CR' may be claimed when subsequent scans suggest small lesions were likely still present and in fact the patient had PR, not CR at the first time point. Under these circumstances, the original CR should be changed to PR and the best response is PR.

² NE=inevaluable

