2.2 Secondary Objectives

2.2.1 To explore whether resistance to BRAF and MEK inhibition is associated with new functional mutations in the approximately 150 oncogenes / tumor suppressor genes that are assessed in more than 10% of the tumors (using NextGen DNA sequencing technology) in the subset of patients who co-enroll in LCCC1108, with particular focus on one of five established resistance genes (BRAF, NRAS, MEK1, MAP3K8 or COT, and PTEN)

2.2.2 To determine the overall response rate (ORR: complete response + partial response) as measured via RECISTv1.1

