3.2.9 Pulmonary embolism on active therapy

3.2.10 History of interstitial lung disease or pneumonitis

3.2.11 Known HIV, Hepatitis B or C infection (with the exception of chronic or cleared HBV and HCV infection, which will be allowed provided the following tests are done at screening: viral hepatitis serology, Hepatitis B surface antigen and Hepatitis B core antibody (IgM) and/or Hepatitis C RNA)

3.2.12 Currently active GI disease, or prior surgery that may affect ability to absorb oral medications

3.2.13 History or current evidence/risk of retinal vein occlusion (RVO) or retinal pigment epithelial detachment (RPED):

- Predisposing factors to RVO or RPED (e.g. uncontrolled glaucoma or ocular hypertension, uncontrolled systemic disease such as hypertension, diabetes mellitus, or history of hyperviscosity or hypercoagulability syndromes)
- Visible retinal pathology as assessed by ophthalmic exam that is considered a risk factor for RVO or RPED such as:
 - Evidence of new optic disc cupping
 - Evidence of new visual field defects
 - Intraocular pressure > 21 mm Hg

3.2.14 Currently receiving cancer therapy (chemotherapy, radiotherapy, immunotherapy, or biologic therapy) **NOTE:** palliative radiation therapy is permitted for non-target lesions that are either new or present at baseline provided total dose does not exceed 30 Gy; however, radiation skin injury has been reported with concurrent use of dabrafenib and radiation. See concomitant medications section 4.5.3 for recommendations when palliative radiation is prescribed.

3.2.15 Use of other prohibited medications within 5 half-lives or 14 days prior to the first dose of study drugs or requires any of these medications while receiving medication on this study (see section 4.5)

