4.6 Duration of Therapy

In the absence of treatment delays due to adverse events, treatment may continue until:

- Disease progression* (*Some patients may remain on treatment after progression (at the discretion of the investigator) as long as they are still experiencing clinical benefit
- In patients without progression, therapy may continue up to 3 years
- Inter-current illness that prevents further administration of treatment
- Unacceptable adverse event(s)
- Patient decides to withdraw from the study, **OR**
- General or specific changes in the patient's condition render the patient unacceptable for further treatment in the judgment of the investigator.

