4.7 Duration of Follow Up

Patients who come off therapy due to progression will enter the follow-up phase every 3 months for up to 1 year from study entry to document survival (no tumor measurement per study protocol will be necessary after progression).

Patients who come off therapy for reasons other than progression will enter the follow-up phase every 3 months for up to 1 year from study entry to document survival. If tumor assessments are available for patients who have not yet experienced progressive disease (PD), these evaluations will be documented in the eCRF until PD is confirmed. Regardless, of the reason that a patient comes off treatment, dermatologic exams will continue every 3 months for the first 6 months following discontinuation from dabrafenib, and may be done by a physician local to the patient. Only after these dermatologic exams are complete is the patient considered off follow-up, even if they do not require survival follow-up for this entire 6 month period.

Patients who come off therapy for reasons other than progression, later receive the dabrafenib/trametinib off-study and then progress on the combination therapy may be re-consented to undergo a progression biopsy. These subjects will then remain on study for safety monitoring, in relation to the biopsy procedure, for 30 days. Subjects who have an ongoing \geq grade 2 or serious AE (SAE) related to the study procedure at 30 days will continue to be followed until the event is resolved or deemed irreversible by the investigator.

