6.0 EVALUATIONS AND ASSESSMENTS

6.1 Time and Events Table

Assessment	Pre-Study ¹ (≤ 21 days except where noted)	D1 Cycle 1	D1 Cycle 2 (+/- 3 days)	D1 Cycle 3 (+/- 3 days)	D1 Cycle 4 (+/- 3 days)	D1 Cycle 5 (+/- 3 days)	D1 Cycle 6 (+/- 3 days)	D1 Cycle 7 (+/- 3 days)	D1 Cycle 8 (+/- 3 days)	D1 Cycle 9 and every other cycle ² (+/- 5 days)	D1 Cycle 9, and every 4 th cycle ² (+/- 5 days)	Yrly ³	End of Treatment (+/- 7 days) ⁴	Follow –up ⁴
Informed Consent	X													
History, PE ⁵	X	X	X	X	X	X	X	X	X	X			X	
Dermatologic exam	X			X		X		X		X ⁶			X ⁶	X ⁶
Ophthalmic exam	X ³											X ³		
ECOG PS	X	X	X	X	X	X	X	X	X	X			X	
Pregnancy Test ⁷	X		Only if clinically appropriate ⁷											
Hematology, serum chemistries, and LFTs ⁸	X	X ¹	X	X	X	X	X	X	X	X			X	
Coagulation studies ⁹	X													
ECG	X			X		X					X			
ECHO	X			X		X					X			
Patient Diary		Review throughout study												
Concomitant Meds	X	Review throughout study											X ⁴	
Toxicity Assessment ¹⁰	X	Review throughout study ¹⁰											X ⁴	X ¹⁰
Tumor measurement ¹¹	X			X		X		X		X ¹²				
Brain Scan ¹¹	X	Only if clinically indicated												
Tumor biopsy ¹³	X ¹³	At time of or after progression ¹³												
LCCC1108 enrollment ¹⁴	X													
Blood Sample ¹⁵		See footnote #15												
Survival Status														X

Key to Time and Events Table 6.1 Footnotes

¹Radiological assessments, physical, dermatologic and ophthalmic exams, EKG and ECHO, as well as laboratory evaluations including hematology, serum chemistries, and LFTs may be performed up to 3 weeks prior to day 1 of treatment. Screening labs performed within 48 hours prior to Cycle 1 Day 1 do not need to be repeated on C1D1.

²Treatment cycles are defined as every 21 days; study site visits are every other cycle after cycle 9. The study window for cycle 9 and beyond is +/-5 days. **Please note:** patients may remain on treatment after progression (at the discretion of the investigator) as long as they are still experiencing clinical benefit (see section 4.1). Patients may continue on study and receive treatment for up to 3 years or death (whichever occurs first) with clinic visits and tumor evaluations as noted in table.

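### The best-response window in Section 6.9.5 runs to end of treatment, not to first RECIST progression, so a response first established after progression could be counted in ORR

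*Combined protocol and SAP*

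**What the plan says.** The secondary objectives (Section 2.2) include ORR: "To determine the overall response rate (ORR: complete response + partial response) as measured via RECISTv1.1". They also include duration of response and PFS, both by RECIST 1.1. Section 6.9.5 sets the window for best response: "The best overall response is the best response recorded from the start of the study treatment until the end of treatment". It then refers to a table of paired time points.

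End of treatment is not the same as progression in this trial. Section 4.1 says: "Patients may remain on treatment after progression (at the discretion of the investigator) as long as they are still experiencing clinical benefit". Section 4.6 repeats this as an exception to stopping at progression. Straight after its own note on treatment past progression, footnote 2 of the Time and Events Table (Section 6.1) adds: "Patients may continue on study and receive treatment for up to 3 years or death (whichever occurs first) with clinic visits and tumor evaluations". Section 6.3.2, which contains the tumor measurements, is scheduled for "Day 1 of every other 3-week cycle starting with Cycle 3 until end of treatment".

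The only text that drops scans after progression is in Sections 4.7 and 6.6: "no tumor measurement per study protocol will be necessary after progression". It applies to patients who come off therapy because of progression. Section 6.4, on continued treatment after progression, only refers the reader to the correlative procedures. Section 8.1 plans a response rate with a 95% confidence interval and says nothing about assessments after PD.

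**The concern.** The window closes at a date that can fall well after RECIST progression, and scans are scheduled in between. Under Section 6.9.3, PR is judged against the baseline sum of diameters and PD against the smallest sum on study. A patient can therefore meet PD and later meet PR numerically.

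If such a response counts, ORR mixes responses before treatment failure with responses after it. In the same patient the response would begin after the PFS event, and duration of response would have no clear end date because the first progression has already happened. Some of these late responses might also not be due to the study drugs alone, since exclusion criterion 3.2.14 notes that "palliative radiation therapy is permitted for non-target lesions that are either new or present at baseline". With the rule unsettled, the analyst would have to choose after seeing the data.

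**Working it through.** The documents state no ORR target, power or precision, so there is no planned figure to reproduce. The check sets the provisions side by side and follows patients through them.

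**Inputs.** Window: start to end of treatment (6.9.5). Treatment past progression allowed (4.1, 4.6, 6.1). Scans every second 3-week cycle from Cycle 3 while on treatment (6.3.2), less often for responders after Cycle 9. PR: sum at least 30% below baseline. PD: sum at least 20% and at least 5 mm above the smallest sum, or a new lesion (6.9.3). Planned n = 20 (1.1).

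**What the table covers.** Its first time points are CR, PR or NE. No row starts with PD, and none starts with SD. Wherever PD is the second time point, the result is SD if the minimum SD duration is met, otherwise PD. The paired layout implies that a PR or CR must be seen twice.

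**Path 1, no new lesion (assumed sums of diameters).**

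| Scan | Sum (mm) | Calculation | Status |
|---|---|---|---|
| Baseline | 100 | – | – |
| Cycle 3 | 75 | 75/100 − 1 = −25% | SD |
| Cycle 5 | 92 | 92/75 − 1 = +22.7%; 92 − 75 = +17 mm | PD |
| Cycle 7 | 68 | 68/100 − 1 = −32% | meets PR |
| Cycle 9 | 68 | −32% | PR repeated |

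With a cut at RECIST PD, best response is SD and the patient is a non-responder. With the window as stated, the Cycle 7 and 9 scans form a PR/PR pair and the patient can be scored PR.

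**Path 2, new lesion.** One PR, then PD from a new lesion, then the lesion resolves and two further scans read PR. The PR/PD row gives SD (or PD). The later PR/PR pair, also inside the window, gives PR. The plan does not say which governs.

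**Path 3, unaffected.** PR at two scans, then PD. The PR/PR row already makes this patient a responder, so later scans add 0 points to ORR.

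**Size.** Effect per affected patient = 100/n percentage points. At n = 20 this is 5.0. Illustrative counts, assumed because the documents give none, with exact (Clopper-Pearson) 95% intervals:

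| Responders | ORR | 95% CI |
|---|---|---|
| 15/20 | 75% | 50.9–91.3% |
| 16/20 | 80% | 56.3–94.3% |
| 17/20 | 85% | 62.1–96.8% |

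One or two such patients would move the estimate by 5 or 10 points, against intervals roughly 35 to 40 points wide.

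**The case against.** The strongest reply is that Section 6.9.5 makes the table operative, not the window sentence alone, and that no row turns PD followed by PR or CR into a response. Rows ending in PD yield SD or PD. Footnote 1 goes the same way: once disease reappears after a true CR, the patient has PD even if the lesions still meet PR against baseline. The missing PD row is weak evidence by itself, because the table also lacks an SD row and is plainly abbreviated. All of this stands. The plan does not say outright that a post-PD response counts; it leaves the sequence unclassified inside a window that includes it.

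A second reply is that RECIST 1.1 is cited for further detail and may settle the matter. That publication is not part of the documents, so this cannot be checked here. Since Section 6.9.5 writes out its own window, the citation does not make clear which rule wins.

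A reader might infer that any patient whose new lesion is irradiated and disappears, with target lesions still at least 30% below baseline, adds 5 points to ORR. The documents do not support that. If PR had already been repeated before PD, the patient is a responder anyway. If PR had been seen once, the PR/PD row demotes the patient, and only a later PR/PR pair could reverse that. Radiation is also not needed for the problem to arise, as Path 1 shows.

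**Conclusion.** There is a real but narrow ambiguity. Under the literal window, a patient without a repeated response before RECIST PD who then meets PR or CR at repeated scans on continued treatment could be counted as a responder. This rests on two readings: that the table's paired time points require repetition, and that the window sentence admits scans after PD because nothing excludes them.

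The effect is 5 percentage points of ORR per affected patient at n = 20. The number affected is not in the documents. None or very few is a reasonable expectation, because the path needs progression, then regression to at least 30% below baseline, then a repeat.

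A reader might go further and conclude that the planned ORR is materially inflated. The documents do not support that: ORR is a secondary estimate with no threshold or decision attached, and its interval is far wider than one patient's contribution. The primary kinome endpoint and its sample size are untouched. The reason to act is consistency between ORR, duration of response and PFS.

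**What to change.** In Section 6.9.5, keep the start of the window and change its end to *first documented RECIST 1.1 progression or end of treatment, whichever is earlier*, with the assessment that shows progression included. Add that assessments after RECIST PD are listed separately and not used for ORR or duration of response.

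The wording should name RECIST progression. Section 4.1 also recognizes clinical progression, and a cut at any documented progression would drop a patient who was called clinically, never met RECIST PD, and later responded. RECIST PD also matches the PFS definition in Section 2.2.4.

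The cost is one phrase and one added sentence. Treatment, visits, scans and sample size do not change, and responses after PD remain visible in the listing.
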